2.2 Secondary estimands

Not applicable.

3 Study design

The study is an international, multi-center, non-comparative, phase IIIb, treatment optimization study of asciminib (randomized 1:1 to either 40 mg b.i.d. or 80 mg q.d.) in adult patients previously treated with 2 or more TKIs. Randomization is only used to have a balance in the allocation of treatment into either asciminib 40 mg b.i.d. or 80 mg q.d.

In patients not achieving MMR at 48 weeks or losing the response after the week 48 assessment up to week 108, asciminib dose may be escalated to 200 mg q.d. if in the investigator's opinion the patient may benefit from the escalation. In addition, there must not be any grade 3 or 4 toxicity while on therapy, or persistent grade 2 toxicity, possibly related to asciminib and unresponsive to optimal management.

[figure not shown]
BCR-ABL1 and **CCI** results are required before increasing asciminib dose, therefore the dose escalation can occur at next scheduled visit upon results review of the prior visit. In patients losing response after the week 48 assessment, the last possible time point to initiate the 200 mg dose will be the week 120 visit to ensure that efficacy and safety of the dose escalation can be sufficiently established during the remaining trial follow up period.

If a dose decrease is required, patients will return to the initial dosing regimen (q.d. or b.i.d.) they were using before the dose increase which was considered tolerable. For this reason, if a patient e.g. escalates from 40 mg b.i.d. to 200 mg q.d., in case of a required dose decrease a use to 80 mg q.d. is not allowed and the patient will continue on 40 mg b.i.d. asciminib.

All patients will be treated for a maximum duration of 144 weeks.

The primary endpoint of the study is MMR rate at 48 weeks. As the ELN 2020 recommendations do not give specific treatment guidance for milestones in 3rd line, the ELN 2020 milestone at twelve months for optimal response in 2nd and 1st line was chosen to define the primary endpoint.

Figure 3-1 Study design

*Treatment assignment to b.i.d. or q.d. (1:1) will be done through Interactive Response Technology (IRT).

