6. Eastern Cooperative Oncology Group (ECOG) performance status (PS) of 0, 1, or 2
7. Adequate end organ function as defined by:
- Total bilirubin $\leq 3 \times$ ULN; patients with Gilbert's syndrome may only be included if Total bilirubin $\leq 3 \times$ ULN or direct bilirubin ≤ 1.5 ULN
 - Serum lipase $\leq 1.5 \times$ ULN. For serum lipase $> \text{ULN} - \leq 1.5 \times \text{ULN}$, value must be considered not clinically significant and not associated with risk factors for acute pancreatitis
 - Alkaline phosphatase $\leq 2.5 \times$ ULN
 - Creatinine clearance ≥ 30 mL/min as calculated using Cockcroft-Gault formula
8. Patients must have the following electrolyte values within normal limits or corrected to be within normal limits with supplements prior to first dose of study medication:
- Potassium (potassium increase of up to 6.0 mmol/L is acceptable at study entry if associated with creatinine clearance* within normal limits)
 - Total calcium (corrected for serum albumin); (calcium increase of up to 12.5 mg/dl or 3.1 mmol/L is acceptable at study entry if associated with creatinine clearance* within normal limits)
 - Magnesium, with the exception of magnesium increase $> \text{ULN} - 3.0$ mg/dL; $> \text{ULN} - 1.23$ mmol/L associated with creatinine clearance* within normal limits
- *calculated using Cockcroft-Gault formula
9. Evidence of typical BCR-ABL1 transcripts [e14a2 and/or e13a2] at the time of screening which are amenable to standardized RQ-PCR quantification

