Grade 2	Recommendation: Maintain dose level, but initiate/intensify appropriate skin toxicity therapy (such as antihistamines, topical corticosteroids and low-dose systemic corticosteroids)
Grade 3, despite skin toxicity therapy	Recommendation: Hold dose until resolved to grade ≤ 1, then: If resolved in ≤ 7 days, reduce dose ↓ 1 dose level If resolved in > 7 days (despite appropriate skin toxicity therapy), discontinue patient from treatment
Grade 4, despite skin toxicity therapy	Mandatory: Permanently discontinue patient from treatment
General disorders and administration site conditions	
Fatigue/Asthenia	
Grade 1 or 2	Recommendation: Maintain dose level
Grade 3	Recommendation: Hold dose until resolved to grade ≤ 1, then: If resolved in ≤ 7 days, maintain dose level If resolved in > 7 days, reduce dose ↓ 1 dose level

All dose modifications should be based on the worst preceding toxicity.
 
^a Common Terminology Criteria for Adverse Events (CTCAE Version 5.0).
 
^b Core LFTs consist of ALT, AST, total bilirubin (fractionated [direct and indirect], if total bilirubin > 2.0 x ULN), and alkaline phosphatase (ALP) (fractionated [quantification of isoforms], if ALP > 2.0 x ULN).
 
^c “Combined” defined as total bilirubin increase to the defined threshold concurrently with ALT/AST increase to the defined threshold.
 
If combined elevations of AST or ALT and total bilirubin do not meet the defined thresholds, please follow the instructions for isolated elevation of total bilirubin and isolated elevation of AST/ALT, and take a conservative action based on the degree of the elevations (e.g. discontinue treatment at the situation when hold dose is needed for one parameter and discontinue treatment is required for another parameter). After all elevations resolve to the defined thresholds that allow treatment re-initiation, re-start the treatment either at the same dose or at one dose lower if meeting a criterion for dose reduction.
	

Dose modifications for asciminib	
Please note that if a patient requires a dose interruption of > 28 days for any toxicity, and > 42 days for hematologic toxicity, then the patient should be discontinued from study treatment	
Worst toxicity CTCAE Version 5.0	Asciminib

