6.6.4.1 Follow up on potential drug-induced liver injury (DILI) cases

Patients with transaminase increase combined with TBL increase may be indicative of potentially severe Drug-induced liver injury (DILI), and should be considered as clinically important events and assessed appropriately to establish the diagnosis. The required clinical information, as detailed below, should be sought to obtain the medical diagnosis of the most likely cause of the observed laboratory abnormalities.

The threshold for potential DILI may depend on the patient's baseline AST/ALT and TBL value; patients meeting any of the following criteria will require further follow-up as outlined below:

- For patients with normal ALT and AST and TBL value at baseline: AST or ALT > 3.0 x ULN combined with TBL > 2.0 x ULN
- For participant with elevated AST or ALT or TBL value at baseline: [AST or ALT > 3 x baseline] OR ALT or AST > 8.0 x ULN], whichever occurs first, combined with [TBL > 2.0 x baseline AND > 2.0 x ULN]

As DILI is essentially a diagnosis of exclusion, other causes of abnormal liver tests should be considered, and their role clarified before DILI is assumed as the cause of liver injury.

A detailed history, including relevant information such as review of ethanol consumption, concomitant medications, herbal remedies, supplement consumption, history of any preexisting liver conditions or risk factors, should be collected.

Laboratory tests should include ALT, AST, TBL, direct and indirect bilirubin, GGT, prothrombin time (PT)/INR, alkaline phosphatase, albumin, and creatine kinase. If available, testing of Glutamate Dehydrogenase (GLDH) is additionally recommended.

Evaluate status of underlying malignancy for an extra-medullary hepatic involvement.

Perform relevant examinations (Ultrasound or MRI, Endoscopic retrograde cholangiopancreatography (ERCP)) as appropriate, to rule out an extrahepatic cause of cholestasis. Cholestasis (is defined as an Alkaline Phosphatase (ALP) elevation > 2.0 x ULN with R value < 2 in patients without bone metastasis, or elevation of the liver-specific ALP isoenzyme in patients with bone metastasis).

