2.7.3 Laboratory data

Clinical laboratory evaluations

All laboratory data will be summarized by visit/time. Shift tables using the low/normal/high/ (low and high) classification will be used to compare baseline to the worst on-treatment value.

Grading of laboratory values will be assigned programmatically as per NCI Common Terminology Criteria for Adverse Events (CTCAE) version 5. The calculation of CTCAE grades will be based on the observed laboratory values only, clinical assessments will not be taken into account.

CTCAE Grade 0 will be assigned for all non-missing values not graded as 1 or higher. Grade 5 will not be used. Details of CTCAE grading and imputation rules are presented in [Appendix 5.3](#).

For laboratory tests where grades are not defined by CTCAE version 5.0, results will be categorized as low/normal/high based on laboratory normal ranges.

On analyzing laboratory data, all sources (central and local laboratories) will be combined. The summaries will include all assessments available for the lab parameter collected no later than 30 days after the last study treatment administration date.

The following summaries will be generated on the corresponding Safety set (SAF, SAF 2) separately for hematology, and biochemistry laboratory data (by laboratory parameter):

- Worst post-baseline CTCAE grade (regardless of the baseline status). Each subject will be counted only for the worst grade observed post-baseline in the on-treatment period.
- Shift tables using CTCAE grades to compare baseline to the worst on-treatment value.
- For laboratory tests where CTCAE grades are not defined, shift tables using the low/normal/high/(low and high) classification to compare baseline to the worst on-treatment value.

The following listings will be produced separately for hematology and biochemistry for the laboratory data:

- Listings of all laboratory data, with CTCAE grades and classification relative to the laboratory normal range. Lab data collected during the post-treatment period will be flagged.
- Listing of all CTCAE grade 3 or 4 laboratory toxicities

Liver function parameters

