Liver function parameters of interest are total bilirubin (TBL), Alanine aminotransferase (ALT), Aspartate aminotransferase (AST) and alkaline phosphatase (ALP). The number (%) of subjects with worst post-baseline values as per Novartis DILI Clinical safety guidelines will be summarized for the criteria defined by single lab parameter. For combination of various parameters, the worst post-baseline values from each single parameter are taken into consideration, i.e. it may not come from the concurrent measurement (i.e. same assessment).

The following summaries will be produced:

- ALT or AST > 3x upper limit of norm (ULN)
- ALT or AST > 5xULN
- ALT or AST > 8xULN
- ALT or AST > 10xULN
- ALT or AST > 20xULN
- TBL > 2xULN
- TBL > 3xULN
- ALT or AST > 3xULN & TBL > 2xULN
- ALT or AST > 3xULN & TBL > 2xULN & ALP \geq 2xULN
- ALT or AST > 3xULN & TBL > 2xULN & ALP < 2xULN

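### The SAP's combined liver rows take each test's worst value at any time, in ULN multiples only, so the ALP split can relabel non-cholestatic cases and the combined count can include subjects who do not meet the protocol's criteria

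*SAP*

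**What the plan says.** SAP 2.7.3 (Liver function parameters) lists single-test rows and three combined rows. For the combinations, "the worst post-baseline values from each single parameter are taken into consideration, i.e. it may not come from the concurrent measurement". The parent row is "ALT or AST > 3xULN & TBL > 2xULN". It is then split at an ALP of 2xULN, and the lower half is "ALT or AST > 3xULN & TBL > 2xULN & ALP < 2xULN". No row refers to baseline or to the R value. Laboratory summaries use values "collected no later than 30 days after the last study treatment administration date", and Protocol Section 3 states "All patients will be treated for a maximum duration of 144 weeks".

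The protocol treats the same pattern differently in three respects.

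- **Timing.** Table 6-4, footnote c, defines a combined elevation as "total bilirubin increase to the defined threshold concurrently with ALT/AST increase to the defined threshold".
- **Baseline.** Section 6.6.4.1 begins "The threshold for potential DILI may depend on" and goes on to name the patient's baseline AST/ALT and bilirubin. Where any of these is raised at entry, bilirubin must exceed both twice baseline and 2xULN, and AST or ALT must exceed 3x baseline or 8xULN. Table 6-4 has a similar rule.
- **Cholestasis.** Table 6-4 (footnote d) and Section 6.6.4.1 call a raised ALP cholestasis only if it is above 2xULN with R below 2. R is ALT divided by ALP, both in ULN multiples. (6.6.4.1 adds an isoenzyme rule for bone metastasis.)

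Inclusion criterion 7 ("Adequate end organ function as defined by") admits total bilirubin up to 3xULN and ALP up to 2.5xULN. The listed limits include none for AST or ALT.

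**The concern.** Taking the worst value is conservative when a criterion asks for a value above a limit. When it asks for a value below a limit, as ALP <2xULN does, taking the worst value makes the criterion harder to meet. The row meant to isolate the non-cholestatic pattern can therefore be emptied by an ALP reading that has nothing to do with the episode.

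The ULN-only limits also ignore the fact that some eligible subjects start above them. A subject who enters with bilirubin over 2xULN and stays there meets the bilirubin half of the combined criterion with no on-study change.

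What is at stake is how the SAP's only combined liver summary is read. Its split into non-cholestatic and cholestatic patterns, and its combined count, can each differ from the cases that sites identify under the protocol's criteria. No planned summary row reconciles the two.

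**Working it through.** The documents give no figure to reproduce. The check is to pass the same patient profiles through both sets of rules.

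**Inputs**

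- SAP 2.7.3: maximum ALT/AST, maximum TBL and maximum ALP over all post-baseline values. The parent row needs ALT/AST >3 and TBL >2 (xULN); the split is at ALP 2. I read worst ALP as highest ALP.
- Period: 144 weeks x 7 + 30 days = 1,008 + 30 = 1,038 days at most. The values combined can be almost that far apart.
- Protocol: same-visit values (Table 6-4, footnote c); baseline-relative limits when AST, ALT or TBL is raised at baseline; cholestasis if ALP >2 and R <2.
- Entry limits: TBL up to 3, ALP up to 2.5.

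**Profiles** (assumed values in xULN, all within the entry limits; baseline ALT, TBL and ALP are 0.8 unless stated)

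| Profile | SAP rows | Protocol rules |
|---|---|---|
| A. ALT 9, TBL 3, ALP 1.2 together; ALP 2.4 at a later visit | Parent, ALP >=2 | Combined case; R = 9/1.2 = 7.5; not cholestatic |
| B. Baseline ALP 2.2, unchanged; ALT 9, TBL 3 | Parent, ALP >=2 | Combined case; R = 9/2.2 = 4.1; not cholestatic |
| C. Baseline TBL 2.5, unchanged; ALT 3.5, ALP 0.9 | Parent, ALP <2 | No case: TBL must exceed 2 x 2.5 = 5.0 |
| D. Baseline TBL 2.5, unchanged; ALT 0.9, ALP 0.9 | No combined row | No case |
| E. ALT 4 at one visit; TBL 2.3 at another; ALP 0.9 | Parent, ALP <2 | No case under the concurrency rule |
| F. ALT 9, TBL 3, ALP 1.2 together, no later rise | Parent, ALP <2 | Combined case, not cholestatic |
| G. ALT 4, TBL 3, ALP 3 together | Parent, ALP >=2 | R = 4/3 = 1.3; cholestatic |

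**Reading the table**

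- F and G agree under both approaches, so the SAP rows work when all three values belong to one episode and baseline is normal.
- A differs from F only by a later ALP value, yet it changes row. B changes row because the SAP has no R value. By the protocol's own bands, A is hepatocellular (R of 5 or more) and B is mixed (R between 2 and 5).
- C and E are counted by the SAP but not by the protocol's rules. D shows the limit of the bilirubin effect: persistent high bilirubin alone reaches only the single-test TBL row, and ALT/AST above 3xULN is also needed.
- Baseline values are not themselves used in these rows. A raised entry value matters only if it persists after baseline.

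**The case against.** The best defence is that the rows are a disclosed screen and that little is really lost. Several parts of it stand.

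- **A reader might infer that a true case disappears.** It does not. Profiles A and B remain in the parent row and appear in the ALP >=2xULN row, and all laboratory data are listed. Under Protocol 6.6.4.1, confirmed cases with no other cause are also reported as SAEs.
- **A reader might infer that the SAP breaks a protocol-specified analysis.** It does not. Protocol 12.5.2 plans no combined liver table. The protocol's criteria sit in the dose-modification and DILI follow-up sections.
- **The protocol is not uniform.** The explicit concurrency wording is only in Table 6-4, footnote c. Section 6.6.4.1 has no ALP condition, so for subjects with normal baseline its limits are those of the SAP parent row, and the worst-value rule captures every such case.
- **Strict same-sample matching has its own fault.** A note to Table 6-4 describes bilirubin rising after a preceding ALT/AST elevation. Same-sample rows alone would drop that sequence.
- **Some context is already planned.** Single-test shift tables from baseline and a listing of medical history relevant to liver dysfunction will help a reader interpret individual subjects.

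These points limit the consequence but do not repair the ALP split, which misclassifies by construction. The shift tables treat one test at a time, so they cannot show whether the elevations belonged to one episode. The sponsor guideline that the SAP cites is attached to the single-parameter criteria and is not supplied, so it does not clearly support the non-concurrent combination.

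**Conclusion.** The concern holds in a limited form. The worst-value rule is acceptable as a screen for ALT/AST with bilirubin. It is unsuitable for the ALP <2xULN row, where an unrelated or persisting ALP of 2xULN or more relabels a non-cholestatic case. It also counts subjects with persisting entry bilirubin between 2 and 3xULN, or with unrelated peaks, whom the protocol's baseline-relative or concurrent criteria would not count.

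The documents give no rates of liver abnormality, at entry or on treatment, so the number of subjects affected cannot be computed. The profiles show only that eligible subjects can be misclassified in both directions. A reader might also infer that a single misplaced case would change the trial's safety conclusion. The documents do not support that, because the table is descriptive and no threshold or test is attached to it. The verdict rests on reading worst ALP as highest ALP, and on taking the protocol's case criteria as the reference for what the split should represent.

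**What to change.** In SAP 2.7.3:

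1. Keep the three worst-value rows and label them as a non-concurrent screen.
2. Add combined rows in which TBL falls on the same sample as the qualifying ALT/AST, or within a stated window after it. Take ALP and R from that episode to classify cholestasis. ALP timing alone is not enough: profile B has an ALP of 2.2xULN in the same sample and is resolved only by R.
3. For subjects with raised baseline AST, ALT or TBL, add a row using the protocol's baseline-relative criteria.
4. List each potential case with its time course of ALT, AST, TBL, ALP and R, including baseline.

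Before programming, the protocol passages must be reconciled. For raised baseline, Table 6-4 takes the lower of the two AST/ALT limits, while Section 6.6.4.1 takes whichever is reached first. Table 6-4 adds a no-cholestasis condition for normal baseline, and 6.6.4.1 has none. Both give cholestasis as R below 2 in the definition but R of 2 or below in the accompanying note. The SAP should state which form it programs and why.

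The cost is that reconciliation, a small amount of programming and a few more table rows. No new data are needed.

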2.7.4 Other safety data

2.7.4.1 ECG and cardiac imaging data

ECG

12-lead ECGs including PR, QRS, QT, QTcF, and RR intervals will be obtained locally for each subject during the study. ECG data will be read and interpreted locally.

The echocardiogram will be performed and evaluated locally to assess the left ventricular ejection fraction (LVEF).

Data handling

The average of the triplicate ECG parameters at each time point will be used in the analyses.

For unscheduled visits, ECGs that are reported on the same day and within 30 minutes apart from each other will be assumed to be sequential ECGs and thus will be used to compute the mean of the ECG parameters.

Unscheduled ECG measurements will not be used in computing the summary statistics for change from Baseline at each post-baseline time point. However, they will be used in the outlier analyses (e.g. QTc > 450 ms, > 480 ms, or > 500 ms at any time point, or an increase from Baseline in QTc > 30 ms or > 60 ms). End of treatment ECG measurements for discontinued subjects will be considered as an unscheduled measurement in case it occurs outside a scheduled visit.

Data analysis

The number and percentage of subjects with notable ECG values will be presented for the corresponding Safety set (SAF, SAF 2). Notable values are defined below:

- QT, QTcF
 - New value of > 450 and \leq 480 ms
 - New value of > 480 and \leq 500 ms
 - New value of > 500 ms
 - Increase from Baseline of > 30 ms to \leq 60ms
 - Increase from Baseline of > 60 ms
- HR
 - Increase from baseline >25% and to a value > 100 bpm
 - Decrease from baseline >25% and to a value < 50 bpm
- PR
 - Increase from baseline >25% and to a value > 200 ms
 - New value of > 200 ms
- QRS
 - Increase from baseline >25% and to a value > 120 ms
 - New values of QRS > 120 ms

A listing of all ECG assessments will be produced and notable values will be flagged. A separate listing of only the subjects with notable ECG values will also be produced. In each listing the assessments collected during the post-treatment period will be flagged.

Change from baseline ECG parameters by timepoint will also be summarized.

A listing of all LVEF assessments will be produced. In the listing, the assessments collected outside of on-treatment period will be flagged.

A summary table with descriptive statistics for LVEF at different timepoints (screening/baseline, Week 48 (+/- 4 weeks) and end of treatment visit) and for change from baseline will be presented. A shift table for LVEF categories ($\leq 40\%$, 41-49%, $\geq 50\%$) at baseline versus worst value on treatment will also be presented.

ECG assessment needs are similar for all subjects up to week 48.

For subjects with dose escalation, ECG assessments will be performed at:

- on the day of dose escalation (pre-dose and between 2h to 3h post-dose ECGs are required),
- two weeks post-dose escalation,
- at next 2 quarterly visits (at 3 and 6 months post-dose escalation),
- every 6 months thereafter.

The above described analyses for ECG data will also be performed separately for a) subjects by dose escalation status (with or without dose escalation) and for b) only for subjects with dose escalation (prior to and after dose escalation).

